## **3 Study Design**

### **3.1 General Design**

Prior to entry into this study, all subjects will sign an Informed Consent and will then undergo a physical assessment including medical history, details regarding their cardiac history, prescription and over-the-counter drug review,, vital signs, electrocardiogram (ECG), evaluation of the major organ systems, hematology, serum chemistries. In addition, female subjects will undergo a serum pregnancy test.

Starting 30 minutes before the cardiac MRI scan (CMR), the subjects will take 16 mgs of ondansetron by mouth. CMR imaging will subsequently take place and then EVP1001-1 will then be administered approximately 15 minutes into the scan for contrast enhanced images. EVP1001-1 will be administered intravenously over approximately one minute. The subjects will each receive 0.28 mL/kg of EVP 1001-1. All subjects will be monitored closely from before ondansetron administration until their discharge from the imaging center. Following MEMRI, delayed-enhanced MRI(DEMRI)is performed using 0.2mmol/kg gadolinium. We will compare the two different contrast enhanced images (EVP1001-1 vs Gadolinium) in determining the viable, peri-infarct, and intra-infarct myocardial tissue.

To ensure a high-quality image, if the participant heart rate is greater than 65 bpm and regular rhythm, metoprolol will be given. If the HR is 65 and irregular, metoprolol will be given if there

are no contraindications (see table 1 below)

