#### Parameters to be Measured:

A standard physical assessment will be performed on the day of imaging (approximately 1-hour post dosing). Body temperature and respiration rate will be measured within 24 hours prior to dosing and at approximately 1- and 2-hours post dose. A standard 12-lead EKG will be performed both before and after the MR study to assure no significant EKG changes have occurred. Patient's hemodynamics will also be serially monitored. A baseline BP and HR will be performed before beginning the study. After EVP1001-1 contrast infusion, BP and HR will be measured every 2 minutes until 10 minutes post EVP1001-1 contrast infusion after which point a BP and HR will be measured every 5 minutes until the conclusion of the MEMRI and every 10 minutes until the conclusion of DEMRI study. There will be a 5-minute post administration observation interval outside the scanner. The patient will also have continuous EKG monitoring during this time. After the study, the patient will have another standard 12-lead EKG performed to compare with the pre-MRI 12-lead EKG. The patient's symptoms will be

CONFIDENTIAL

This material is the property of Stanford University. Do not disclose or use except as authorized in writing by the study sponsor

reassessed 1 hour after infusion of the EVP1001-1 contrast. A differential and serum chemistry profile (with liver function test) will be performed within a month prior to administration of EVP1001-1 and within 24 hours post EVP1001-1. Adverse events (AEs) and discomforts will be recorded until discharge from the imaging center. At the 24 hour follow-up, the subject will be evaluated by telephone to determine if any AEs occurred from the time the subject left the imaging center. The subjects will have a contact number to report any AEs or to ask questions. Any clinically relevant changes from baseline in vital signs, ECG rhythm, clinical chemistries or physical condition and all AEs will be followed until resolution or until the outcome is known. Injection-associated discomforts will be recorded during administration and until imaging is completed. Primary efficacy will be based on determining whether the heart is normal or abnormal and if abnormal whether there is an infarction, ischemia or both. This provides the basis for calculating sensitivity, specificity, accuracy and predictive values. In addition, the location, size, conspicuity and associated confidence for any disease will be recorded.

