### **3.2 Primary Study Endpoints**

The key endpoints of this study include the assessment of safety, tolerance and efficacy of EVP1001-1. Safety and tolerance will be evaluated based on the nature and extent of AEs and injection-associated discomforts and changes in laboratory parameters, vital signs and ECG after administration of EVP1001-1. Effects, if any, of EVP1001-1 on QT/QTc intervals will be determined by comparing the intervals before and after EVP1001-1 across the full HR range for each patient, including use of individual correction of QT by RR. All subjects who receive EVP1001-1 will be included in the analyses. Pre- and post-dose results will be compared for vital signs, clinical laboratory parameters, ECG parameters and hemodynamic parameters to identify individual changes from baseline and potential systematic shifts. The presence or absence of infarcts and/or ischemic areas relative to the current clinical standard (by echo and gadolinium-based cardiac MRI) along with comparison to patient outcomes will determine efficacy.

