#### **4.3 Subject Recruitment and Screening**

This is an open-label, baseline-controlled study to be conducted. Adult male or non-pregnant female patients who have been referred for evaluation of cardiomyopathy and atrial fibrillation and patients who have received stem cell therapy related to these indications will be recruited. An initial cohort study of 6 patients to conduct safety evaluation was conducted before proceeding with 120 additional patients. In the initial cohort, a patient was dosed based on the Phase 1 and 2 clinical trial data evaluation completed by Eagle Vision Pharmaceutical, Inc. Subjects were excluded if they had received an investigational device within 30 days prior to administration of EVP1001-1; had a history of drug abuse or alcoholism; were taking a digitalis preparation; had a history of torsades; had NYHA Grade IV heart failure; had abnormal liver function tests or a history of liver disease; had uncontrolled hypertension; had abnormal calcium, potassium or hemoglobin values at baseline; if they develop a cardiac arrhythmia prior to or during either of the exercise tests-- EVP1001-1 was not administered. The same parameters will apply to the new group of subjects.

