As for intravenous injection of any investigational drug, competent personnel and emergency facilities must be available to address severe and possibly delayed reactions after administration of EVP1001-1 or severe responses to the stress prior to EVP1001-1 administration. Subjects will be observed for AEs starting with the pre-treatment (with ondansetron), during and for at least 1 hour after EVP1001-1 administration during which time emergency equipment will be readily available. AEs will be recorded until discharge from the imaging center. At the 24-hour follow-up, the subject will be evaluated by telephone to determine if any AE occurred from the time the subject left the imaging center. In addition, the subjects will have a contact number to report any AE or to ask questions. Any clinically relevant changes from baseline in vital signs, ECG rhythm, clinical chemistries or physical condition and all AEs will be followed until resolution or until the outcome is known. AEs, if any, will be recorded on the CRF (case report form) along with the action(s) required, time of onset, duration, intensity, and outcome. A judgment will be made by the investigator as to the causality of each event. If a subject has more than one incidence of a given AE, that AE with the greatest severity will be used for analyses. If a cluster of AEs are related, a term describing the syndrome or overall adverse experience should be captured.

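### Ischemia is part of the primary efficacy classification, but the described procedures give no rule for calling it and schedule no reference to judge it against

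*Combined protocol and SAP*

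**What the plan says.** Section 3.1, under Parameters to be Measured, defines primary efficacy as a classification of each heart: "Primary efficacy will be based on determining whether the heart is normal or abnormal and if abnormal whether there is an infarction, ischemia or both". It continues: "This provides the basis for calculating sensitivity, specificity, accuracy and predictive values". Section 3.2 sets the comparator: "The presence or absence of infarcts and/or ischemic areas relative to the current clinical standard (by echo and gadolinium-based cardiac MRI"), and the same sentence adds patient outcomes.

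The imaging sequence is in section 3.1, General Design: "CMR imaging will subsequently take place and then EVP1001-1 will then be administered approximately 15 minutes into the scan for contrast enhanced images". Delayed-enhanced MRI with gadolinium follows. The purpose of the comparison is stated there too: "We will compare the two different contrast enhanced images (EVP1001-1 vs Gadolinium) in determining the viable, peri-infarct, and intra-infarct myocardial tissue". Section 6 (Study Procedures) adds nothing and points back to section 3. Section 7.2 plans a t-test on infarct and viable myocardium.

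Two other sections assume a procedure that section 3.1 does not describe. Section 4.3 withholds the agent for an arrhythmia arising "prior to or during either of the exercise tests", and says the initial cohort's rules carry over to new subjects. Section 8.2 asks for readiness to handle "severe responses to the stress prior to EVP1001-1 administration".

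**The concern.** A diagnostic accuracy figure needs a positivity rule for the new test and a reference result for the same condition in the same patient. For infarct, the plan has a scan on each side. For ischemia it names the category and stops. If the study is run as section 3.1 describes, readers would have to make ischemia calls without a criterion, and the reference would have to be chosen after the fact or left empty.

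This matters because the category sits in primary efficacy. A heart called abnormal on ischemia alone also changes the top-level normal/abnormal result, so the problem is not confined to a sub-table.

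**Working it through.** No figure in the plan depends on this point, so there is nothing to reproduce. The check sets what an accuracy estimate needs beside what the documents supply.

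| Needed | Infarct | Ischemia |
|---|---|---|
| Named in primary efficacy | Yes (3.1, 3.2) | Yes (3.1, 3.2) |
| Index-test measurement | MEMRI defect (3.1, 7.1) | None described |
| Scheduled reference | Delayed gadolinium enhancement (3.1) | None: no stress, perfusion or echo step in 3.1 |
| Class in the image comparison | Yes (3.1) | No |
| Planned analysis | t-test (7.2) | None |

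1. **What the two scans are said to show.** Sections 1.1 and 1.4 describe the agent's uptake as independent of perfusion and as a marker of viable cells. Section 1.3 treats delayed gadolinium enhancement as the benchmark for non-viable tissue. On the protocol's own account, one scan marks viability and the other marks scar. How either would produce an ischemia call is not explained.

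2. **What this does to the estimates.** Sensitivity = TP/(TP+FN) and specificity = TN/(TN+FP). Each of the four counts needs both an index call and a reference call. For ischemia neither is defined, so none of the four can be filled from the procedures in section 3.1.

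3. **How far it reaches.** The classification has 2 × 2 = 4 outcomes: normal, infarction only, ischemia only, and both. Assigning any of them requires an ischemia decision, since normal and infarction only each require ischemia to be ruled out. Collapsing over ischemia leaves infarct present (infarction only or both) against infarct absent (normal or ischemia only). That is the split for which section 3.1 schedules scans on both sides.

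4. **Whether a stress step exists.** Section 3.1 describes none; sections 4.3 and 8.2 presuppose one. Section 3.2 also plans a QT analysis over a range of heart rates within each patient, with no step described that would generate that range. A procedures flowchart is listed in section 14, but its content is not in the text available for review. The conflict cannot be settled from the documents.

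5. **Why the peri-infarct region is not a ready substitute.** Section 7.1 states that the difference between MEMRI and DEMRI represents this region, and section 1.1 says the same of the scar volumes. Scoring MEMRI against DEMRI for a region defined by their disagreement would be circular.

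**The case against.** The strongest reply is that the plan does name comparators for ischemia. Section 3.2 lists echo and patient outcomes beside gadolinium MRI, section 3.3 lists wall motion deficits, and section 1.4 says that earlier DEMRI studies by the same group related ischemia to later events. Sections 4.3 and 8.2 may also reflect a real stress step that the flowchart would show.

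Part of this stands. It rules out three stronger readings that a reader might infer:

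- *That the trial has no stress step.* The text contradicts itself; it does not establish absence. Nothing says that the wording in sections 4.3 and 8.2 is a leftover.
- *That ischemia cannot be evaluated, or that metoprolol hides it.* No section says ischemia is visible only under stress. Metoprolol is conditional on heart rate and a contraindication screen, and its stated purpose is image quality.
- *That the bias can be quantified.* Assuming a rate of MEMRI ischemia calls with no reference positives merely hands that assumption back as a specificity loss. It also sits badly with the observation that no MEMRI ischemia class is described.

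The rest does not answer the point. Section 3.1 schedules no echo. Patient outcomes are not mapped to ischemia. Wall motion is a secondary item with no stated link to an ischemia call. Section 1.4 does not say how ischemia was assessed, and no such method is carried into section 3.1.

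**Conclusion.** The point holds as a gap in the primary efficacy definition combined with an unreconciled contradiction about stress. As described, the ischemia category has no index-test criterion and no scheduled reference standard. Its sensitivity, specificity and predictive values are not interpretable, nor is any normal/abnormal call that rests on ischemia alone.

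The size is structural: one of the two conditions in the primary classification lacks a defined measurement. The MEMRI–DEMRI comparison of infarct and viable tissue is unaffected. The conclusion assumes that section 3.1, to which section 6 defers, is the full procedure. A flowchart or imaging manual that schedules an ischemia assessment and a reference would change it. The point should be corrected before efficacy is analysed, but it does not undermine the rest of the study.

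**What to change.** First reconcile section 3.1 (both parts), section 3.2, section 4.3 and section 8.2 on whether a stress step exists. Section 4.3 contains a rule for withholding the agent and section 8.2 an emergency-readiness statement. Neither should be deleted merely to tidy the endpoint, and which text is right is for the sponsor to decide.

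Unless that reconciliation shows a scheduled ischemia assessment with a call rule and a reference:

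- Remove ischemia from the primary efficacy classification in sections 3.1 and 3.2.
- Base sensitivity, specificity, accuracy and predictive values on presence or absence of infarct against gadolinium MRI, and add that analysis to section 7.2 with a stated rule for presence on each scan.
- Report ischemia information from clinical records descriptively.
- Report the peri-infarct region as a measured MEMRI–DEMRI volume difference, not as accuracy against DEMRI.

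The cost is an amendment to a primary efficacy definition, with no added patients or procedures. The trial gives up a primary ischemia claim that the described procedures do not support.

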#### *Primary Objective*

Specific Aim 1 evaluates the efficacy of MEMRI-DEMRI to characterize the peri-infarct injury in the ventricles and atria.

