### **3.3 Secondary Study Endpoints**

In addition, location, size, conspicuity, confidence, wall motion deficits and related diagnostic information will be assessed.

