## 7 Statistical Plan

### 7.1 Sample Size Determination

The total number of 0 patients will power this study adequately, however as we have extended the protocol to include the atrial fibrillation participants (and extra 60 pts) the difficulty in imaging the atria, coupled with the thin atrial walls, means that we expect a difference in DEMRI volume of 40 (+ or - 20) in participants with early disease and 60 (+ or - 20) in participants with advanced disease. Accordingly, 60 participants will be needed for the additional cohort. Our published pre-clinical study in 13 swine demonstrated the infarct volume percentage difference of 9% between MEMRI and DEMRI ( $p<0.001$ ). This difference will enable significant delineation of the changes in the peri-infarct viability between the cell therapy and control arms. The preliminary porcine data presented above demonstrated a mean of 100% increase in the CNR of the peri-infarct region and a mean of 50% decrease in the scar volume, suggesting robust MEMRI signal detection of stem cell engraftment and increased peri-infarct viability. Furthermore, the clinical trial in 6 ICM patients demonstrated significant difference in the infarct volume between MEMRI defect and DEMRI enhancement. This difference between MEMRI and DEMRI represents PIR assuring reliable detection of the PIR. Employing these data, in order to detect a mean difference of 20% in MEMRI signal of stem cell engraftment and MEMRI-DEMRI signal of peri-infarct viability with a standard deviation of 5%, the t-test sample size calculation in this study has 90% power at the alpha 0.05 significance level, assuming an equal variance between the two distributions.

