### 7.2 Statistical Methods

Student's t-test to compare MEMRI and DEMRI measurement of the infarct and viable myocardium. Pearson's correlation to generate any association between stem cell engraftment/peri-infarct viability and functional restoration and/or clinical outcome.

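### Sensitivity is scored per heart with no location match, so a MEMRI defect in the wrong wall counts as a true positive and sensitivity can exceed location-correct detection

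*Combined protocol and SAP*

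**What the plan says.** Section 3.1, under Parameters to be Measured, sets the unit of scoring: "Primary efficacy will be based on determining whether the heart is normal or abnormal and if abnormal whether there is an infarction, ischemia or both". The next sentence ties the accuracy measures to that call: "This provides the basis for calculating sensitivity, specificity, accuracy and predictive values". Location follows as something noted alongside: "In addition, the location, size, conspicuity and associated confidence for any disease will be recorded".

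Section 3.2 judges efficacy on "The presence or absence of infarcts and/or ischemic areas relative to the current clinical standard (by echo and gadolinium-based cardiac MRI", together with patient outcomes. Section 3.3 places location among the secondary endpoints: "In addition, location, size, conspicuity, confidence, wall motion deficits and related diagnostic information will be assessed".

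The aim is regional. The Primary Objective reads "Specific Aim 1 evaluates the efficacy of MEMRI-DEMRI to characterize the peri-infarct injury in the ventricles and atria". Section 3.1 compares the two contrasts for viable, peri-infarct and intra-infarct tissue. Section 7.3 sets a goal of better sensitivity and specificity for viable myocardium and the peri-infarct region (PIR). The analysis named in section 7.2 is "Student's t-test to compare MEMRI and DEMRI measurement of the infarct and viable myocardium", plus a Pearson correlation.

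**The concern.** The primary score asks whether an infarct is present in the heart. The aim asks whether MEMRI identifies the right tissue. A per-heart yes/no cannot separate a MEMRI defect that lies on the reference infarct from one that lies elsewhere, because both are recorded as infarct present by both methods.

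Two consequences follow. Sensitivity, read as evidence that MEMRI finds the infarct, may include patients in whom it marked different myocardium. And in a heart that is reference-positive, a false extra defect is never an error: the heart is already a true positive, and whole-heart specificity is computed only in reference-negative hearts.

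Sections 1.1 and 1.4 expect the accuracy evaluated here to be the basis for pivotal studies. A sensitivity figure carried forward as regional evidence would claim more than the score can show.

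**Working it through.** **Inputs**

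- Scoring unit: the heart (section 3.1).
- Role of location: recorded alongside (3.1), secondary endpoint (3.3).
- Reference: echo and gadolinium MRI (3.2), with no rule for matching by wall, segment or territory.
- Expected sensitivity and rate of misplaced defects: not in the documents. Values of s and f below are assumptions.
- The plan's own figure: none for sensitivity. The power statement in section 7.1, "has 90% power at the alpha 0.05 significance level", concerns a t-test on signal with mean difference 20% and SD 5%. Taking alpha as two-sided, the normal approximation gives 2 × (1.96 + 1.282)² × 5² / 20² = 1.31, so 2 per group (about 3 using the t distribution). It neither sizes nor constrains a diagnostic measure.

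**Step 1: apply the rule to two hypothetical patterns**

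| Reference | MEMRI | Whole-heart score | Location-matched reading |
|---|---|---|---|
| Anteroseptal infarct | Inferolateral defect only | True positive | Infarct missed, plus a false finding |
| Anteroseptal infarct | Anteroseptal defect plus a spurious lateral one | True positive | Infarct found, plus a false finding |

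**Step 2: the excess**

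Among patients with a reference infarct, let s be the probability that MEMRI marks the correct location, and f the probability that it marks a defect elsewhere when the true infarct is missed. A heart is called positive in either case, so

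whole-heart sensitivity = s + (1 - s)f

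excess over location-correct sensitivity = (1 - s)f

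The excess cannot be negative. It is zero when f = 0 and at most 1 - s.

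**Step 3: assumed values**

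| s | f | Whole-heart sensitivity | Excess (points) |
|---|---|---|---|
| 0.90 | 0.05 | 0.90 + 0.10 × 0.05 = 0.905 | 0.5 |
| 0.80 | 0.10 | 0.80 + 0.20 × 0.10 = 0.82 | 2 |
| 0.70 | 0.20 | 0.70 + 0.30 × 0.20 = 0.76 | 6 |
| 0.60 | 0.30 | 0.60 + 0.40 × 0.30 = 0.72 | 12 |

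With 50 reference-positive patients (also an assumption), the third row gives 50 × 0.76 = 38 true positives instead of 50 × 0.70 = 35.

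**Step 4: would another planned analysis catch it?**

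The t-test in section 7.2 compares amounts. The pilot in section 1.1 reports scar of 39% by delayed-enhanced MRI (DEMRI) and 16% by MEMRI, a difference of 23 points. A MEMRI defect of 16% gives the same 23 points wherever it lies. The correlation is with function or outcome, not with position. The 16-segment model appears only in the porcine work (section 1.3).

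**The case against.** Per-patient sensitivity is a legitimate quantity and not a biased estimate of something else. If the only question were whether a patient has an infarct, the rule would be acceptable. This stands, and it is why the point is limited to regional claims.

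The phrase in section 3.2 about infarcts and ischemic areas is plural and could be read area by area. That is possible, but it supplies no matching rule, and section 3.1 ties sensitivity explicitly to the heart-level call.

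Other assessments would make misplacement visible in the data: the tissue comparison in 3.1, the measurements in 7.2, and location and size in 3.3. None of them is a location-matched score, so visibility would not become a counted error.

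A reader might infer something much stronger. If the pilot's 39% and 16% are taken as about 6 and 3 of 16 segments, a defect placed at random in every patient scores 100% under the written rule. Yet at least 2 of its 3 segments fall in the reference infarct with probability only 170/560 = 0.304. The arithmetic is right, but the documents do not support using it as the size of the problem. It describes a reader who calls infarct in everyone. Enrolment includes dilated cardiomyopathy and atrial fibrillation, so infarct-negative hearts can be expected, and the specificity required by 3.1 would expose such a reader there. The pilot's negligible uptake within the infarct (1.1, 1.4) and the consistent anteroseptal pattern in swine (1.3) also point away from random placement. No section reports a wrong-wall or spurious MEMRI defect.

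**Conclusion.** The point holds as a gap in the scoring rule. Relative to location-correct detection, sensitivity can be overstated and never understated, and extra false defects in reference-positive hearts go uncounted. Over the assumed pairs the excess is about 0.5 to 12 percentage points, and it is zero if no defect is misplaced. Because the documents give neither s nor f, this range is illustrative and not an estimate.

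A reader might conclude that the reported sensitivity will be inflated. The documents do not establish that; it depends on wrong-wall defects occurring. What they do establish is that the whole-heart call alone cannot support the regional aim in section 2 or the goal in section 7.3, and that no planned analysis fills the gap.

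**What to change.** In sections 3.1, 3.2 and 7.2, prespecify a location-matched efficacy analysis:

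- Score MEMRI and the reference as positive or negative in each segment or territory, separately for infarct and for ischemia. The 16-segment model could serve for the ventricles, with predefined regions for the atria.
- Report segment-level sensitivity, specificity, accuracy and predictive values, with confidence intervals clustered by patient. Scoring all segments keeps true negatives; a count of matched and unmatched infarcts alone would not, and so could not give specificity, accuracy or negative predictive value.
- MEMRI defects are expected to be smaller than DEMRI scar, so some segments will disagree for that reason alone. Also report the share of patients whose MEMRI defect lies mainly within the reference infarct, with the overlap rule fixed before images are read.
- Keep the whole-heart result alongside, and base claims about regional viability or PIR on the location-matched result.

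The cost is modest. No new scan or patient is needed, since location is already to be recorded. It must, however, be recorded by segment or region for both MEMRI and the reference, which the documents do not yet say. Atrial regions need their own definition, the clustered analysis is slightly more work, and reported sensitivity may be lower.
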